Title: Breast capsular contracture following post-mastectomy reconstruction in women treated with the leukotriene inhibitor zafirlukast

Patient population: Patients who will be undergoing mastectomy with immediate tissue-expander reconstruction

Background

Primary objective:

- a) Compare capsular thickness by gross and microscopic measurement at the time of expander-implant exchange in those treated with zafirlukast (20 mg PO BID) compared with standard of care

Secondary objectives:

- a) Perform histologic analysis of the capsule specimens to compare overall fibrosis and collagen deposition between the zafirlukast and standard of care groups

Exploratory objectives:

- a) The capsule tissue that is removed at the time of expander-implant exchange will be fixed and histologically assessed for the presence of fibroblasts and myofibroblasts.

Study design:

We propose a 2-arm, 90 patient (45 per cohort) trial in patients who will be undergoing mastectomy with immediate tissue-expander reconstruction to determine whether treatment with zafirlukast (20 mg PO BID) can reduce or prevent the development of capsular contracture. All patients undergoing mastectomy with immediate tissue-expander placement will be approached in clinic at the time of their initial consultation with the plastic surgeon and enrolled in the trial at this point. Approximately 60 women undergo mastectomy with tissue-expander reconstruction at our institution per year, thus enrollment will occur over a two-year period.

Number of patients:

90 total: 45 per cohort factoring in a 10% attrition rate

Duration of therapy:

In the absence of treatment delays due to adverse events, treatment may continue until tissue expansion is complete or until:

- Illness that prevents further administration of treatment
- Unacceptable adverse event(s)
- Patients decides to withdraw from the study
- Significant patient non-compliance with protocol
- General or specific changes in the patients' condition render the patient unacceptable for further treatment in the judgment of the investigator.

Duration of follow up:

Patients are routinely followed for two years after undergoing implant-based reconstruction. In this study, we will initially see patients periodically for research visits until tissue expansion has been completed. After implant exchange, we will see patients every 2 weeks for the first month, and every month for the subsequent 4 months. We will then see them every 6 months for the remainder of the two years. Those patients who are removed from treatment will be followed as per our standard of care, which is monthly for the first six months and then every six months for two years. Serious adverse events will be collected for 30 days after the end of treatment, or until death, whichever occurs first. Patients removed from the study for unacceptable treatment-related adverse event(s) will be followed until resolution or stabilization of all treatment-related adverse events to Grade 1 or baseline.

Study drugs:

Zafirlukast 20mg PO BID

Safety assessments:

Safety will be assessed by reviewing adverse events (AEs), laboratory evaluations, physical examination, and spontaneous report. Each patient will be assessed periodically for the development of any toxicity. All AEs and serious AEs (SAEs) will be documented and reported. We will also pay particular attention to adverse events of clinical interest specific to zafirlukast.

Unique aspects of this study:

This is the first study to prospectively investigate the potential of zafirlukast to slow or prevent capsular contracture from occurring.

List of Abbreviations

AE	adverse event
ALP	alkaline phosphatase
ALT	alanine aminotransferase
ANC	absolute neutrophil count
AST	aspartate aminotransferase
BUN	blood urea nitrogen
CBC	complete blood cell (count)
CHR	Committee on Human Research (UCSF IRB)
CR	complete response
CRC	Clinical Research Coordinator
CRF	case report form
CSF	cerebral spinal fluid
CT	computerized tomography
CTCEA	Common Terminology Criteria for Adverse Events
CTEP	Cancer Therapy Evaluation Program
CTMS	Clinical Trial Management System
DFS	disease-free survival
DLT	dose limiting toxicity
DSMC	Data and Safety Monitoring Committee
DSMP	Data and Safety Monitoring Plan
FDA	Food and Drug Administration
GCP	Good Clinical Practice
HDFCCC	Helen Diller Family Comprehensive Cancer Center
HGB	Hemoglobin
HIV	human immunodeficiency virus
ICH	International Conference on Harmonization
IND	investigational new drug application
IP	investigational product
IRB	Institutional Review Board

1 INTRODUCTION

1.1 Background on Indication

The majority of women who undergo mastectomy for breast cancer will choose expander-implant reconstruction. Unfortunately, breast implants are frequently complicated by the development of

capsular contracture¹. Contracture formation is an excessive foreign body reaction that results in a tight and hard fibrous capsule around the implant. This causes distortion of the breast, displacement of the implant, and in more severe cases, pain and limited range of motion. Reported rates in the literature of women affected by this condition range from 3 to 50%²⁻⁴. However, these percentages likely under-represent the actual number of women affected as this complication may develop long after a patient is regularly evaluated by the plastic surgeon.

Radiation therapy increases the likelihood of capsular contracture^{1-3,5,6}. Women who have been irradiated face contracture rates upwards of 20%⁷⁻⁹. Unfortunately, many women who require mastectomy and implant reconstruction for breast cancer had radiation in the past or will require radiation therapy in the future, thus putting them at greater risk for this complication.

The treatment of capsular contracture is primarily surgical, requiring removal of the implant, excision of the capsule, and replacement of the implant. However, excision of the capsule and implant replacement does not guarantee contracture will not recur, and many women face repeated operations.

Recent research has focused on methods to decrease capsule formation¹⁰⁻¹³. These include: altering the properties of implants¹⁴⁻¹⁶, coating the implants¹⁷, fat grafting the capsule¹⁸, inserting acellular dermal matrix^{19,20}, treating with anti-estrogens²¹ and treating with leukotriene receptor antagonists (LTAs)^{22,23}. The goal of many of these interventions is to actually prevent capsular contracture from even occurring.

1.2 Background on the Compounds

1.2.1 Zafirlukast

Zafirlukast is a synthetic, selective peptide leukotriene receptor antagonist (LTRA), with the chemical name 4-(5-cyclopentyloxycarbonylamino-1-methyl-indol-3-ylmethyl)-3-methoxy-N-*o*-tolylsulfonylbenzamide. It is a selective and competitive receptor antagonist of leukotriene D4 and E4 (LTD4 and LTE4), components of slow-reacting substance of anaphylaxis (SRSA). Cysteinyl leukotriene production and receptor occupation have been correlated with the pathophysiology of asthma, including airway edema, smooth muscle constriction, and altered cellular activity associated with the inflammatory process, which contribute to the signs and symptoms of asthma. Patients with asthma were found in one study to be 25-100 times more sensitive to the bronchoconstricting activity of inhaled LTD4 than non-asthmatic subjects. *In vitro* studies demonstrated that zafirlukast antagonized the contractile activity of three leukotrienes (LTC4, LTD4 and LTE4) in conducting airway smooth muscle from laboratory animals and humans. Zafirlukast prevented intradermal LTD4-induced increases in cutaneous vascular permeability and inhibited inhaled LTD4-induced influx of eosinophils into animal lungs. Inhalational challenge studies in sensitized sheep showed that zafirlukast suppressed the airway responses to antigen; this included both the early-and late-phase response and the nonspecific hyper-responsiveness. In humans, zafirlukast inhibited bronchoconstriction caused by several kinds of inhalational challenges. Pretreatment with single oral doses of zafirlukast inhibited the bronchoconstriction caused by sulfur dioxide and cold air in patients with asthma. Pretreatment with single doses of zafirlukast attenuated the early-and late-phase reaction caused by inhalation of various antigens such as grass, cat dander, ragweed, and mixed antigens in patients with asthma. Zafirlukast also attenuated the increase in bronchial hyper-responsiveness to inhaled histamine that followed inhaled allergen challenge.

1.3 Rationale for the Proposed Study

The development of capsular contracture is multifactorial²⁴⁻²⁶ with histologic studies demonstrating the primary role of inflammatory cells in this process. Peptide growth factors and inflammatory cytokines are reactivated by the presence of an implant, leading to a persistent sub-acute

inflammatory response ultimately resulting in capsular contracture²⁷⁻²⁹. As inflammation is induced as part of normal healing, as well as by the ongoing presence of an implant, pharmacologic inhibition of inflammation is an appealing target in preventing capsular contracture from developing. The control of inflammation has been an underlying factor in successful treatment^{26,30}.

Cysteinyl leukotrienes play a role in the activation and up-regulation of capsular contracture mechanisms³¹⁻³³. Grella et al. demonstrated that in women with severe capsular contracture (Baker grade III/IV) there was marked up-regulation of cysLTR mRNA and protein compared to women with implants who did not develop capsular contracture³². Treatment with leukotriene receptor antagonists thereby presents a novel mechanism in the potential prevention of capsular contracture. Zafirlukast specifically inhibits LTC4, LTD4 and LTE4 and has a presumed suppressive effect on myofibroblasts. Several studies have looked at the effects of leukotriene inhibitor administration on capsular contracture in animal models, and found decreased capsule formation following treatment^{22,34}. Histologic analysis of capsules in rats treated with zafirlukast demonstrated thinner capsules with decreased collagen fibers^{34,35}.

There are descriptive studies of patients treated with LTAs as an off-label use for capsular contracture³⁶⁻⁴⁰. Women who have developed capsular contracture who are subsequently treated with standard dosing of LTAs show decreased capsule contracture based on clinical assessment^{36,38,40}. However, there have been no studies to date evaluating the biology behind this observation in humans. Based on an evidence-based analysis by Cheng et al., further prospective randomized studies are needed to determine the efficacy and safety of leukotriene inhibitors as a potential treatment of capsular contracture¹⁹. No studies are prospectively investigating the potential of zafirlukast to slow or prevent capsular contracture from occurring.

2 OBJECTIVES OF THE STUDY

2.1 Primary objective

- Compare capsular thickness by gross and microscopic measurement at the time of expander-implant exchange in those treated with zafirlukast (20 mg PO BID) compared with standard of care

2.2 Secondary objectives

- Perform histologic analysis of the capsule specimens to compare overall fibrosis and collagen deposition between the zafirlukast and standard of care groups

2.3 Exploratory objectives

- The capsule tissue that is removed at the time of expander-implant exchange will be fixed and histologically assessed for the presence of fibroblasts and myofibroblasts.

3 STUDY DESIGN

3.1 Characteristics

We propose a 2-arm, 90 patient (45 per cohort) trial in patients who will be undergoing mastectomy with immediate tissue-expander reconstruction to determine whether treatment with zafirlukast (20mg PO BID) can reduce or prevent the development of capsular contracture. All patients undergoing mastectomy with immediate tissue-expander placement will be approached

in clinic at the time of their initial consultation with the plastic surgeon and enrolled in the trial at this point. Approximately 60 women undergo mastectomy with tissue-expander reconstruction at our institution per year, thus enrollment will occur over a two-year period.

Patients will be block randomized 1:1 into two cohorts: treatment with zafirlukast and the standard of care, or standard of care alone. Patients will begin treatment with zafirlukast on post-operative day one (+/- 5 days) following placement of tissue expander(s) after the participant is determined safe from a surgical recovery standpoint. They will be continued on the standard dosing (20mg PO twice per day) of zafirlukast through expander fill. Last dose of Zafirlukast will be administered the day prior to expander implant exchange procedure. Patients will be seen every 1 to 2 weeks for expander fill, and will be assessed clinically (refer to section 6.2 for research visits). The treating physician will determine the frequency of visits based on each patient's expander need.

During expander-implant exchange, three representative sections of the expander capsule will be collected: medial, lateral and anterior capsule specimens. These specimens will be bisected; half will be sent to pathology and half will be collected by the [name] lab. Gross and microscopic determination of capsule thickness will be performed by the pathology department. The [name] lab will fix and stain the tissues to look for the presence of collagen, level of fibrosis, and number of myofibroblasts. Fibrosis level and collagen presence will be determined by performing immunohistochemistry with a Trichrome stain of the tissues, as well as Western blot analysis with Collagen-1. Myofibroblasts will be detected using immunohistochemistry with commercially available antibodies.

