3.3.1 Inclusion Criteria

1. Patients who are scheduled to undergo therapeutic or prophylactic mastectomy with immediate placement of tissue expanders and have a strong family history or hereditary cancer
2. Age \geq 18 years
3. Zafirlukast is pregnancy category B. There are no adequate and well-controlled trials in pregnant women. Therefore, the effects of zafirlukast on the developing human fetus are unknown. For this reason, women of child-bearing potential must agree to use adequate contraception: 2 methods of birth control, prior to study entry and for the duration of study participation. Should a woman become pregnant or suspect she is pregnant while she is participating in this study, she should inform her treating physician immediately.
4. Ability to understand a written informed consent document, and the willingness to sign it
5. At least 4 weeks post-completion of chemotherapy
6. Adequate organ function within 14 days start of study start:
 - a. Absolute neutrophil count (ANC) \geq 1.5 X 10⁹/L
 - b. Hemoglobin (Hgb) \geq 9g/dL
 - c. Platelets (plt) \geq 100 x 10⁹/L
 - d. Potassium within normal range, or correctable with supplements;

- e. AST and ALT $\leq 2.5 \times$ Upper Limit Normal (ULN) or $\leq 5.0 \times$ ULN if liver tumor is present
- f. Serum total bilirubin $\leq 1.5 \times$ ULN
- g. Serum creatinine $\leq 1.5 \times$ ULN, or 24-hr clearance $\geq 60\text{ml/min}$

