3.3.2 Exclusion Criteria

1. Any significant medical condition, laboratory abnormalities, which places the subject at unacceptable risk if he/she were to participate in the study
2. Currently on a leukotriene inhibitor or used within the past 6 months
3. Prior chest wall radiation
4. Pregnant or breastfeeding
5. Hepatic impairment as defined by:
 - AST(SGOT) $> 2.5 \times$ institutional ULN and ALT(SGPT) $> 2.5 \times$ institutional ULN
6. Has known psychiatric or substance abuse disorders that would interfere with cooperation with the requirements of the trial.

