9.0 STATISTICAL CONSIDERATIONS AND EVALUATION OF RESULTS

Determination of sample size and accrual rate

Sample size calculated to be 82 (41 per arm) based on a two-tailed alpha of 0.05, with a beta of 0.18. With a possible 10% attrition rate, the sample size is increased to 90 (45 per arm). As approximately 60 patients undergo mastectomy with immediate tissue expander placement per year at Mt. Zion, it is expected that roughly 80% of these women will be enrolled in the study.

The determination of sample size is based on the assumption that treatment with the leukotriene inhibitor zafirlukast will decrease capsule thickness in women with tissue expanders at the time of implant exchange. Based on the reported results from literature review, a capsule thickness of >2.4mm would be considered undesirable and <1.2mm would be considered desirable. We assume the capsule thickness is <1.2mm under zafirlukast as the target efficacy of clinical importance for the study population and an efficacy of 50% reduction in capsule contracture between two cohorts would be considered clinically meaningful. Under the t-test with a 2-sided alpha of 5%, we will need 45 evaluable patients in each cohort to have >80% power to detect an

improvement in capsule thickness from average 2.4mm (sd 2mm) to average 1.2mm (sd 2mm). Specifically, the study hypothesis is defined as:

H0: $\mu_1 \geq \mu_0$ (The capsule thickness of the cohort A is greater than capsule thickness of the cohort B versus

H1: $\mu_1 < \mu_0$ (The capsule thickness of the cohort A is greater than capsule thickness of the cohort B.

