9.1 Analyses Plans

This is an intention to treat analysis. All patients who were randomized will be evaluated.

Data will be summarized using descriptive statistics by study cohorts. For continuous variables, descriptive statistics will include the number of non-missing values, mean, standard deviation, median, minimum and maximum. For categorical variables, descriptive statistics will include counts and percentages per category by study cohorts.

Primary analysis:

The primary objective of the trial is to determine the capsule contracture between the two study cohorts and the primary efficacy outcome in this trial is capsule thickness at the time of expander-implant exchange. Capsule thickness will be determined by averaging thickness from three separate specimens per patient. The capsule thickness will be analyzed by study cohorts, and t-tests and descriptive statistics with mean, standard deviation and 95% confidence intervals will be used for significance. Missing data will not be imputed. An alpha level of 0.05 will be considered significant for the primary endpoint. For exploratory analysis, the primary endpoint of capsule thickness will be presented as mean \pm SEM and evaluated using analysis of variance (ANOVA) with factors including study cohort, radiotherapy and length of drug treatment.

Secondary Analysis:

For secondary objectives of the trial, we will determine the level of fibrosis and presence of collagen from the biopsy specimens. The level of fibrosis and the presence of collagen will be analyzed descriptively as continuous levels and as ordinal levels with mean, standard deviation and 95% confidence intervals. The difference in the level of fibrosis and relative presence of collagen between study cohorts will be compared using t-tests for significance.

Similar statistical methods will also be employed to analyze the capsule tissue that is removed at the time of expander-implant exchange to determine the level and presence of collagen, fibroblasts and myofibroblasts.

Confounding Factors:

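### Radiotherapy is treated as affecting the capsule and may be given on study, yet randomisation is unstratified and the valid but unadjusted primary t-test gives up some precision

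*Combined protocol and SAP*

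**What the plan says.** - **Radiotherapy as a factor.** Section 1.1: "Radiation therapy increases the likelihood of capsular contracture". Section 3.3.2 excludes "Prior chest wall radiation". Section 9.1 returns to radiation twice, in the exploratory ANOVA and under confounding factors.
- **Radiotherapy on study.** Section 6.9 prohibits only chemotherapy and biological therapy. Section 6.7 lets the investigator give whatever treatment is thought necessary. Because earlier chest wall radiation is excluded, the radiotherapy factor in 9.1 can sensibly mean only radiation given during the study.
- **Population.** Section 3.3.1 admits "Patients who are scheduled to undergo therapeutic or prophylactic mastectomy with immediate placement of tissue expanders".
- **Allocation.** Section 3.1: "Patients will be block randomized 1:1 into two cohorts: treatment with zafirlukast and the standard of care, or standard of care alone". Section 6.3 repeats block randomisation. Neither names a stratum. Section 6.2 places randomisation on the day of surgery and tells surgeon and patient the cohort straight afterwards.
- **Analysis.** The primary comparison in 9.1 is a t-test of mean thickness by cohort. As an exploratory analysis, thickness is "evaluated using analysis of variance (ANOVA) with factors including study cohort, radiotherapy and length of drug treatment". The confounding-factors paragraph adds univariate screening and results by radiation subgroup.

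**The concern.** A trial that names a strong influence on its outcome would normally balance the arms on a baseline variable that predicts it, and carry that variable into the primary model. Here neither is done. If more irradiated patients fall into one arm by chance, the sponsor has an unadjusted primary result and no primary estimate that takes the imbalance into account.

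The exploratory ANOVA fills that gap poorly. It uses radiotherapy actually received, which is settled after randomisation when everyone knows the assignment. It also includes length of drug treatment, which exists only in the zafirlukast arm and so cannot be cleanly separated from cohort. At stake are precision in a trial with little power to spare and the ease of interpreting its estimate.

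**Working it through.** **Inputs from section 9.0.** Two-sided alpha 0.05; difference 2.4 − 1.2 = 1.2 mm; SD 2 mm per arm; 45 evaluable per arm; also 41 per arm before the 10% attrition allowance.

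**Assumptions, not in the documents.** Proportion irradiated before exchange p = 20–40% (30% for the power figures); effect on thickness g = 1–2 mm; radiotherapy only in therapeutic cases; share of therapeutic cases q = 50%, 70% or 85%.

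**1. The plan's own power.** SE = 2 × √(2/45) = 0.422 mm; noncentrality = 1.2/0.422 = 2.85; t-test power = 80.4%, so the stated figure above 80% reproduces. At 41 per arm, SE = 0.442 mm and power = 76.5%. (Section 9.0 attaches a beta of 0.18 to 41 per arm, which does not reproduce; that is a separate matter.)

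**2. Chance of imbalance.** For two independent Binomial(45, p) counts with p = 20%, 30%, 40%:
- arms differ by at least 10 percentage points: 23%, 30%, 33%
- arms differ by at least 15 percentage points: 9%, 13%, 16%

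Blocking fixes the arm sizes but does not constrain a covariate outside the blocks.

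**3. Size of the shift.** Shift = imbalance × g. A 15-point imbalance gives 0.15 × 1 = 0.15 mm to 0.15 × 2 = 0.30 mm. That is 13–25% of the 1.2 mm target, or 0.15/0.422 = 0.36 to 0.30/0.422 = 0.71 of one standard error.

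**4. Validity.** Simulation with no drug effect, 41 per arm, 40,000 runs: type I error of the unadjusted t-test is 5.0–5.1% overall. Among runs with an imbalance of at least 15 points it is 7.6% (p = 30%, g = 1.2 mm) or 12.7% (p = 30%, g = 2.0 mm).

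**5. Variance due to radiotherapy.** Share = p(1 − p)g²/4. Over p = 20–40% this is 4–6% for g = 1 mm and 16–24% for g = 2 mm. At p = 30% it is 5.25% and 21%.

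**6. What stratifying on indication recovers.** If only therapeutic cases are irradiated, indication explains a fraction f = p(1 − q)/[q(1 − p)] of the variance in radiotherapy. For q = 50%, f = (0.3 × 0.5)/(0.5 × 0.7) = 43%. Residual SD = 2 × √(1 − f × share). Power, with one degree of freedom spent on the stratum:

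| q | f | 45 per arm, g = 1 / 2 mm | 41 per arm, g = 1 / 2 mm |
|---|---|---|---|
| 50% | 43% | 81.2% / 83.9% | 77.5% / 80.3% |
| 70% | 18% | 80.7% / 81.9% | 76.9% / 78.1% |
| 85% | 8% | 80.5% / 81.0% | 76.7% / 77.2% |

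At 45 per arm and p = 30%, balancing indication lowers the chance of a 15-point radiotherapy imbalance from 13% to about 4%, 9–10% and 12% for the three values of q.

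**7. Ceiling.** A covariate that predicted radiotherapy perfectly (p = 30%) would give 83.3% (g = 1.2 mm) or 88.6% (g = 2.0 mm) at 45 per arm, and 79.7% or 85.5% at 41. Radiotherapy planned before surgery could come nearer to this than indication does.

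**The case against.** The strongest reply is that nothing is broken. Randomisation makes the t-test valid, and chance imbalance is already inside its standard error. If the SD of 2 mm is total between-patient variation, the planned power already allows for radiotherapy. The plan also names radiotherapy in advance as an ANOVA factor. The prevalence and effect are assumed: section 1.1 speaks of likelihood of contracture, not of millimetres, and an effect of 2 mm would exceed the drug's whole target. Removing patients who need chemotherapy or biological therapy (6.9) may also thin out the irradiated group.

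All of this stands as a limit on the size of the point. It does not remove the point, because adjusting for a baseline predictor costs almost nothing and the existing ANOVA is not a baseline-adjusted primary estimate.

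Three stronger readings are tempting and are not supported:
- A reader might infer that imbalance biases the primary test or would pass for a drug effect. Overall type I error stays at about 5%, and even a 15-point imbalance moves the estimate by less than one standard error under these assumptions.
- A reader might infer that the only remedy in the plan is a data-driven search for covariates. Section 9.1 does contain such screening, but it also prespecifies the radiotherapy ANOVA.
- A reader might put endocrine therapy on the same footing, since 1.1 lists "treating with anti-estrogens" among researched ways to reduce capsule formation. The protocol gives no effect size and no analysis uses it, but 6.7 already records such drugs as concomitant medication.

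**Conclusion.** The point holds as one of efficiency and interpretability, not of validity. The plan leaves a named influence on the outcome out of both the randomisation and the primary model, although a baseline proxy for it can be recorded before randomisation.

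The likely gain from using indication is modest: at most about 3.5 percentage points of power at 45 per arm and 4 at 41, and well under 1 point if 85% of cases are therapeutic. It is largest when prophylactic cases are about half of the sample. That radiotherapy falls only on therapeutic cases is a clinical inference that the documents do not state. The absence of a stratum and of a baseline-adjusted primary estimate rests on the text alone.

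**What to change.** - **Sections 3.1 and 6.3.** Stratify the block randomisation by one binary factor recorded before surgery. Either use mastectomy indication, counted as therapeutic if either breast is therapeutic and otherwise prophylactic, or use planned post-mastectomy radiotherapy (yes/no) if that is recorded before surgery. The either-breast rule is needed because a patient may receive more than one expander. Table 6 lists no field for the factor, so add one at screening.
- **Section 9.1.** Make the primary analysis a linear model of thickness on cohort plus that stratum, and keep the unadjusted t-test as a sensitivity analysis.
- **Radiotherapy received.** Keep it as an exploratory descriptor, not a primary covariate, and record its dates on the CRF, since 6.7 asks for medications only. Endocrine drugs need no new field.

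Cost: one extra randomisation list and one degree of freedom (88 to 87 at 45 per arm). Eligibility, treatment and sample size do not change.
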